## 9.0 Study Withdrawal/Discontinuation

Subjects who are non-compliant with the study protocol, or no longer wish to participate in the study will be withdrawn from the study.

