## 6.0 Study Procedures

The design is a randomized, double-blind (except for those in the diet group), placebo-controlled study. Once the subject is determined to be eligible, we will randomly assign him/her to one of the study arms (diet, spironolactone, chlorthalidone, or placebo) as depicted in **Figure 1**. Each subject will be treated for 8 weeks. During the study, subjects will receive (1) a diet containing 6 g salt per day, (2) oral administration of spironolactone (50 mg per day), (3) oral administration of chlorthalidone (25 mg/day) or (4) oral administration of matching placebo. All medications and matching placebo will be prepared and dispensed by Vanderbilt's Investigational Drug Services (IDS). Except for the diet arm, the investigators and the study subjects will be blinded to the treatment. NaMRI, Pulse wave velocity (PWV) and a hyperinsulinemic euglycemic clamp (HEGC) study will be performed at the beginning and at the end of the study. An optional DNA blood sample may also be collected.

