**Figure 1: Study Protocol**

**Safety Precautions:** In this protocol we have the following safety precautions: (1) Anti-hypertensive/diuretic medications (like the ones used in this study) may lower blood pressure excessively and/or alter serum electrolyte levels. Accordingly, we will monitor blood pressure and electrolyte levels throughout the study. Subjects who develop electrolyte imbalance will receive an electrolyte supplement or be asked to slightly change their diet. (2) Since the use of diuretics during pregnancy introduces unnecessary risk, female subjects will have a urine pregnancy test at each study visit before any research procedures are performed. (3) Since the presence of any metal introduces unnecessary risk, a screening X-ray exam will be performed to confirm the absence of any metal in subjects where that is a possibility.

**Permanent stopping criteria:** A patient will be terminated from the study for any of the following reasons:

- Persistent hyperkalemia ( $K > 5.5$  mmol/L) occurs;
- Any allergies to the drugs develop;
- Women who become pregnant;
- There are any adverse events or clinical events that the PI judges increases the risk to the patient;
- There are any signs or symptoms of decline or deterioration of their health status.

**Screening Visit:** Within about two weeks up to the start of the Treatment Phase (which begins after the Baseline Visits) and after the subject has provided informed consent, the following information will be collected:

- Demographics
- Medical history
- Concomitant medications

Also, the following procedures and assessments will be performed:

- Vital signs (including blood pressure)
- Physical exam

- CMP (comprehensive metabolic panel) unless there is a documented CMP within 1 month of the stipulated study entry date as part of routine medical care
- Pregnancy test
- X-ray exam

**Baseline Visits (Week 0):** Subjects that qualify for the study will be randomized to one of the study arms, and will be asked to come in a fasted state on two separate days (preferably consecutive but no more than about 4 weeks apart) to the General Clinical Research Center (GCRC). On one of the visits, a hyperinsulinemic euglycemic clamp (HEGC) study will be performed. At the other visit, NaMRI and pulse wave velocity (PWV) will be performed, as well as a hand grip test. These procedures are described below.

At the Baseline Visits, the following information will be collected:

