- Concomitant medications (medication reconciliation)
- Medical history and concurrent illnesses

Also, the following procedures and assessments will be performed:

- Pregnancy test
- Vital signs (including blood pressure)
- CMP (including electrolytes)
- Blood samples for research labs, which include hsCRP, IL-6, TNF $\alpha$ , F2-isoprostanes, ADMA, s-ICAM, s-VCAM, insulin, leptin, adiponectin, resistin, C-peptide, lipid panel, FFA, and immune cell analysis
- Urine samples for research labs

Subjects in the diet arm will be counseled on the details of the low salt diet. Subjects in the other arms will be dispensed study drug. After the second Baseline visit, the intervention phase of the study begins.

**Week 2 Visit:** At the Week 2 Visit, subjects will be asked to come to the GCRC. The following information will be collected:

- Concomitant medications
- Adverse Events (AEs)

Also, the following procedures and assessments will be performed:

- Pregnancy test
- Vital signs (including blood pressure)
- CMP (including electrolytes)
- Urine samples for research labs
- Dietary counseling for those in the diet arm

**Week 4 Visit:** At the Week 4 Visit, subjects will be asked to come to the GCRC. The following information will be collected:

- Concomitant medications
- Adverse Events (AEs)

Also, the following procedures and assessments will be performed:

- Pregnancy test
- Vital signs (including blood pressure)
- CMP (including electrolytes)
- Urine samples for research labs
- Dietary counseling for those in the diet arm
- Study drug dispensing for those in the other arms

**Week 8 Visits:** At the Week 8 Visit, subjects will be asked to come in a fasted state on two separate days (preferably consecutive but no more than about 4 weeks apart) to the GCRC. On one of the visits, a hyperinsulinemic euglycemic clamp (HEGC) study will be performed. At the other visit, NaMRI and pulse wave velocity (PWV) will be performed, as well as a hand grip test. These procedures are described below.

- Concomitant medications
- Adverse Events (AEs)

Also, the following procedures and assessments will be performed:

- Pregnancy test
- Vital signs (including blood pressure)
- Physical exam
- CMP (including electrolytes)
- Blood samples for research labs, which include hsCRP, IL-6, TNF $\alpha$ , F2-isoprostanes, ADMA, s-ICAM, s-VCAM, insulin, leptin, adiponectin, resistin, C-peptide, lipid panel, FFA, and immune cell analysis
- Urine samples for research labs

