**Diet Recalls:** For subjects in the diet arm, study dietitians will conduct dietary recalls via telephone interviews after the Screening Visit, as well as at Week 4 and at Week 8 to confirm compliance with the low-salt diet. We will utilize a two-day diet recall that includes one week day and one weekend day to capture variability in eating. Dietary recall data will be collected and analyzed using Nutrition Data System for Research. For subjects in the other arms, dietitians will conduct the dietary recalls 2 times—after the Screening Visit and at Week 8.

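### Section 9.0 withdraws non-compliant subjects, but only the diet arm has a treatment-compliance check, so withdrawal can tilt the diet contrasts and a null spironolactone result would be hard to interpret

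*Combined protocol and SAP*

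**What the plan says.** Section 9.0 (Study Withdrawal/Discontinuation) reads: "Subjects who are non-compliant with the study protocol, or no longer wish to participate in the study will be withdrawn from the study". It covers every arm, is mandatory in form, and neither defines non-compliance nor sets a threshold.

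Section 6.0, Diet Recalls, gives the diet arm a recall after Screening, before the diet starts, and then further recalls "as well as at Week 4 and at Week 8 to confirm compliance with the low-salt diet". For the rest it says: "For subjects in the other arms, dietitians will conduct the dietary recalls 2 times", after Screening and at Week 8. Those recalls record food, not tablets.

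For the pill arms, Section 6.0 says: "All medications and matching placebo will be prepared and dispensed by" the investigational pharmacy. The Week 4 Visit lists "Study drug dispensing for those in the other arms", and the Schedule of Procedures shows dispensing at Weeks 0 and 4. No return of unused tablets, count, diary, adherence question or drug level appears in the visit lists, the Schedule of Procedures or Section 10.0.

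The Schedule of Procedures places the sodium MRI, the primary endpoint, at Weeks 0 and 8 only. Section 10.0 compares each pair of arms by two-sample t-test. It defines no analysis set and no handling of withdrawn subjects.

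**The concern.** A rule that removes subjects after randomisation is neutral between arms only if it can find its targets equally well in each. Here, failure to follow the assigned treatment is looked for in one arm out of four. Diet subjects found off the diet at Week 4 can be withdrawn before the only post-baseline MRI. Pill-arm subjects who take nothing can stay in and contribute a Week 8 value.

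Two separate things are at stake:

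- **Bias in contrasts with diet.** The diet mean would lean towards subjects who adhered, while the pill-arm means would include everyone.
- **Interpretation of the primary hypothesis.** Aim 2 asks whether spironolactone lowers tissue sodium. If it shows no difference from placebo, the trial will hold no direct record of whether the tablets were taken.

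**Working it through.** **1. Which contrasts are exposed.** Four arms give 4 × 3 / 2 = 6 pairwise tests. Diet is in three of them (against placebo, spironolactone and chlorthalidone). The other three compare pill arms with one another. Those arms share the same visits, dispensing and recalls, so the rule finds non-takers equally poorly in each.

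**2. The plan's own figure.** Section 10.0 assumes a 5 mmol/L reduction in muscle sodium, SD 6.0, 85% power and a Bonferroni-adjusted two-sided level of 1%, and gives 41 per group. A noncentral-t calculation needs 40 per group at 0.01 and 41 at 0.05/6 = 0.0083, the Bonferroni level for six tests. The figure reproduces. Only the 5 mmol/L is carried forward.

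**3. Size of the tilt.** Assumptions, none of them given in the documents:

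- a share *f* in each active arm does not adhere and gets no effect;
- adherers get 5 mmol/L under either treatment;
- a fraction *p* of diet non-adherers is detected, withdrawn and lost to the analysis;
- all pill-arm non-adherers stay in;
- adherers and non-adherers are otherwise alike.

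Pill arm, everyone analysed: 5(1 − f).

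Diet arm, after losses: 5(1 − f) / (1 − f·p).

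Apparent gap: the second minus the first.

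For f = 20%:

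- p = 100%: 4.0/0.80 − 4.0 = 5.0 − 4.0 = **1.0 mmol/L**
- p = 50%: 4.0/0.90 − 4.0 = 4.44 − 4.0 = **0.44 mmol/L**
- p = 25%: 4.0/0.95 − 4.0 = 4.21 − 4.0 = **0.21 mmol/L**

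The same formula for other shares gives these gaps in mmol/L:

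| Non-adherent share | p = 100% | p = 50% | p = 25% |
|---|---|---|---|
| 10% | 0.50 | 0.24 | 0.12 |
| 20% | 1.00 | 0.44 | 0.21 |
| 30% | 1.50 | 0.62 | 0.28 |

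The same amounts are added to the diet-versus-placebo estimate relative to its as-randomised value, provided placebo subjects are all kept.

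**4. What could stand in for adherence data.** Section 6.0 says "we will monitor blood pressure and electrolyte levels throughout the study", as a safety precaution, with measurements at Weeks 0, 2, 4 and 8 in all arms. It also lists "Urine samples for research labs" without naming analytes. None of these is assigned an adherence purpose, and Section 10.0 plans no analysis of adherence.

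**The case against.** Several points against the concern stand.

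- **A reader might infer that the rule can act only on diet.** It cannot be read that narrowly. It covers non-compliance with the whole protocol, so missed visits, missed procedures or a volunteered report of not taking tablets could trigger it in any arm. What is missing is a systematic tablet check.
- **A reader might infer that the primary contrast is biased.** The asymmetry does not bias it: spironolactone and placebo are blinded and follow the same procedures.
- **A reader might infer that the gap costs power.** If 20% took no tablets, the effect would fall from 5 to 4 mmol/L and power at 41 per group and 0.83% from 85% to 62%. But this dilution occurs whether or not tablets are counted, and it remains once non-adherent subjects are kept in. It is not a consequence of the missing check. At 50 per arm (200 subjects, equal allocation assumed), the corresponding figures are 93% and 74%.
- **Full detection is unlikely.** It rests on two-day telephone recalls, and the Week 8 recall falls around the time of the endpoint MRI, when removal may come too late to lose the outcome. The documents also do not say that data from withdrawn subjects are discarded, so an analysis among diet compliers is an inference.
- **A null result would not be wholly opaque.** Section 6.0 expects the drugs to affect blood pressure and electrolytes, and both are measured. Pharmacy accountability outside these documents cannot be seen.

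These points limit the size and reach of the concern. They leave in place a mandatory rule with unequal detection, an endpoint measured only at Week 8, and no statement on withdrawn subjects.

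**Conclusion.** The concern holds in a limited form. Withdrawal for treatment non-compliance is likely to fall mainly on the diet arm, and this can tilt the three contrasts with diet in its favour. At 20% non-adherence the upper bound is 1.0 mmol/L against an assumed effect of 5. With partial detection the figure is 0.44 (half) or 0.21 (a quarter). These values depend on the assumed shares, on zero effect in non-adherers and on loss of the withdrawn subjects' endpoints.

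For spironolactone against placebo the problem is interpretation, not bias: no planned data distinguish an ineffective drug from one not taken, and electrolytes and blood pressure are only indirect, non-specific signals. The change should be made, because adherence not recorded during treatment cannot be recovered later.

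**What to change.** **Section 9.0.** Replace the non-compliance clause with text to this effect:

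> *Measured non-adherence to the assigned diet or tablets is recorded and does not by itself withdraw a subject in any arm. Such subjects still have the Week 8 measurements and are analysed in the arm to which they were randomised.*

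Withdrawal at the subject's own wish stays. The permanent stopping criteria in Section 6.0 are left unchanged.

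**Section 10.0.** State that the Aim 2 comparisons are made as randomised, regardless of measured adherence.

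**Section 6.0 and Schedule of Procedures.** Add a returned-tablet count at Weeks 4 and 8 in the spironolactone, chlorthalidone and placebo arms. Record adherence in every arm, from the existing recalls in the diet arm. The count helps to interpret the result; it does not recover power.

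**Cost.** A short protocol amendment, minutes of site or pharmacy time at visits that already take place, and one data field.

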## 10.0 Statistical Considerations

**Power and sample size calculations:** For Aim 1, 100 per race group (200 in total) provides 85% power to detect an effect size of 0.42 in blood pressure, forearm blood flow or PWV with two-sided type I error = 5%. For Aim 2, assuming a reduction in muscle Na+ of 5 mmol/L and SD=6.0 mmol/L by drug treatment, 85% power and Bonferroni adjusted 2-sided type I error (significant level) test at level 1%, a sample size of 41 subjects per group (161 in total) is needed. For Aim 3, the proposed sample size 200 enable us to detect the Pearson Correlation of 0.21 or higher (absolute value) between Na+ storage change and immune cell activity change with two-sided type I error = 5%. For Aim 4, the sample size calculation is the same as Aim 3.

**Data collection and analysis:** For Aim 1, summary statistics of blood pressure, forearm blood flow and PWV at week 0 will be provided for both African American group and Caucasian group. We will test the difference of these variables among two race group using two sample t-test. For Aim 2, we will conduct univariate analysis for comparing the magnitude of the Na+ tissue content among each pair of treatment groups using two sample t-test, and the Bonferroni correction will be applied to control the type I error due to multiple comparisons. In addition, partial linear model will be used to estimate the linear treatment effect and interaction effect while adjusting the nonlinear effect such as age and gender. For Aim 3, we will calculate the Pearson correlation of Na+ storage change (before and after treatment) and the immune cell activity change. Alternatively, Spearman correlation or Kendall's tau will be calculated to capture the nonlinear correlation. We will also perform linear regression with all covariates and pairwise interactions in the model to adjust the impact of factors such as age, sex, and body weight on tissue sodium. For Aim 4, we focus on the association between tissue sodium change and insulin sensitivity change using the same analysis methods as in Aim 3.

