missing link towards a new and better understanding of the chronic pro-inflammatory state that leads to cardiovascular disease with aging (Fig. 1). Similarly, Na+ stored in muscle may predispose to energy deficit and insulin resistance. Tissue Na+ storage thus may not only be pathophysiologically linked to arterial hypertension, but also with diabetes mellitus, another highly relevant cardiovascular risk factor. Successful therapeutic bending of the slope relationship between age and tissue Na+ accumulation (Fig. 1) therefore promises to become a novel, important approach for cardiovascular disease prevention.

In this clinical project, we will take the first step towards therapeutic “bending” of the age/Na+ accumulation relationship to a flatter slope (Fig. 2). We will establish a cohort of 200 subjects with pre-hypertension, age: 30 to 80 years. The cohort will be controlled for

gender, race, and age so that cross-sectional analysis of the cohort characteristics will provide us with new information on the effect of race on tissue Na+ content (Aim 1, Fig. 2). In a prospective, double-blinded randomized-controlled trial, we then will test the hypothesis that 8 weeks of a reduced salt diet or drug treatment with either the MR antagonist spironolactone, or with the diuretic hydrochlorothiazide, will reduce skin and muscle Na+ content (Aim 2, short-term longitudinal readout, Fig. 2). Tissue Na+ content will be our primary endpoint in Aims 1 and 2. As secondary endpoints, we will read out differences in blood pressure, skin forearm blood flow by BOLD MRI, and arterial stiffness by measurement of pulse wave velocity. Finally, we speculate that lower tissue Na+ content reduces a pro-inflammatory immune cell phenotype and improves insulin sensitivity (Aims 3 and 4). We will address the following specific aims:

- Specific Aim 1:** To test the hypothesis that African Americans are characterized by increased tissue Na+ storage, which is paralleled by higher blood pressure, reduced forearm blood flow, and enhanced pulse wave velocity
- Specific Aim 2:** To test the hypothesis that treatment with spironolactone reduces tissue Na+ content (Primary Outcome)
- Specific Aim 3:** To test the hypothesis that Na+ storage leads to immune cell activation (Secondary Outcome)

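### Aim 2: six pairwise tests at a 5% family-wise level mean 0.83% per test and 164 subjects, not the printed 1% and 161, and the plan leaves open whether skin Na+ is a separate primary endpoint

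*Combined protocol and SAP*

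**What the plan says.** Section 10.0 sizes Aim 2 on muscle Na+ alone. It assumes a 5 mmol/L reduction, an SD of 6.0 mmol/L and 85% power, and gives "Bonferroni adjusted 2-sided type I error (significant level) test at level 1%, a sample size of 41 subjects per group (161 in total". The analysis paragraph of the same section compares Na+ content "among each pair of treatment groups using two sample t-test" and adds that "the Bonferroni correction will be applied to control the type I error due to multiple comparisons". It gives neither the divisor nor a family-wise level for Aim 2; 5% two-sided is stated for Aims 1 and 3. Sections 5.0 and 6.0 define four arms: diet, spironolactone, chlorthalidone and placebo.

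Section 2.0 describes the endpoint more broadly. Tissue Na+ "content will be our primary endpoint in Aims 1 and 2", and the hypothesis is that diet, spironolactone, "or with the diuretic hydrochlorothiazide, will reduce skin and muscle" Na+. The MRI paragraph in section 6.0 labels the measurement of both tissues as the primary endpoint. The formal statement of Aim 2 is narrower: "To test the hypothesis that treatment with spironolactone reduces tissue" Na+ "content (Primary Outcome". It names one drug and no comparator.

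**The concern.** The printed level and total do not follow from the analysis described beside them: 1% is not 5% divided among six pairs, and 161 is not four groups of 41.

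The less visible problem is what the correction covers. Section 10.0 reads as six muscle comparisons. Section 2.0 and the MRI paragraph can be read as making skin a primary endpoint in its own right, which would double the number of tests. The spironolactone label in Aim 2 points to a much smaller family. Depending on the reading, the same threshold is conservative, about right or too lenient. If the choice is made after Na+ results are known by arm, the error rate attached to the primary claim cannot be stated.

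**Working it through.** **Inputs.** From section 10.0: difference 5 mmol/L, SD 6.0 mmol/L (standardised effect 5/6 = 0.83), power 85%, two-sided test. From section 5.0: four arms. Assumed: 5% family-wise level for Aim 2, and equal arms.

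**Number of tests and level.** Pairs of four arms: 4 × 3 / 2 = 6. Bonferroni: 0.05/6 = 0.00833. The printed 1% equals 0.05/5, and four arms cannot give five pairs.

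**Reproducing 41 per group.** The normal approximation is n = 2 × [SD × (z for 1 − α/2 + z for 0.85) / difference]². It gives 37.6 (38) at 1% and 38.9 (39) at 0.83%. The two-sample t-test (noncentral t), which is the planned test, gives:

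| Per-test level | n per group for 85% power | Rounded up | × 4 | Power at 41 | Power at 50 |
|---|---|---|---|---|---|
| 1% | 39.27 | 40 | 160 | 86.8% | 93.6% |
| 0.05/6 = 0.83% | 40.66 | 41 | 164 | 85.4% | 92.7% |
| 0.05/12 = 0.42% | 45.93 | 46 | 184 | 79.1% | 88.8% |

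The printed 41 is the exact t-test answer at 0.83%, not at 1%.

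**Total.** 4 × 41 = 164, and 161/4 = 40.25. Four times the unrounded n is 157.1 at 1% and 162.7 at 0.83%, so neither gives 161. The difference is 3/164 = 1.8%.

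**Family-wise error for six pairs in one tissue.** At 1% the Bonferroni bound is 6 × 0.01 = 6%. Pairwise tests share arms and are correlated, so the actual rate is lower. Simulation under no effect with 41 per arm gives 4.8–4.9% at 1% and 4.1–4.2% at 0.83%.

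**Family-wise error if each tissue is tested separately.** These come from 100,000 simulated null trials with 41 per arm. The correlation between tissues was varied from 0.7 (lower figure) to 0 (higher figure), because the documents give none.

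| Family, both tissues | Tests | At 0.83% | At 1% | At 0.05/number of tests |
|---|---|---|---|---|
| All six pairs | 12 | 7.28–8.06% | 8.50–9.55% | 3.96–4.23% |
| Three active arms vs placebo | 6 | 4.08–4.46% | 4.80–5.34% | 4.08–4.46% |
| Spironolactone vs placebo | 2 | 1.48–1.73% | 1.76–2.04% | 4.33–4.96% |

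Only the first family clearly exceeds 5% at the level the plan uses.

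**If success requires both tissues.** No split of alpha across tissues is needed, but power falls. At 0.83% with 41 per arm and the same standardised effect in skin, power for both tissues is 0.854 × 0.854 = 0.73 if they are independent. It cannot exceed 0.854.

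**The case against.** Much of the case on the other side stands. Section 10.0 prints its other significance levels as whole percentages, and 41 per group is what 0.83% requires. The calculation very probably used six tests, with the level rounded for print. The 5% behind 0.83% is itself an assumption for Aim 2. The slip in the total is under 2%, and planned enrolment is 200.

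Three stronger readings are tempting, and the documents do not support them.

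- A reader might infer that testing at 1% breaches 5% for the analysis as sized. It does not: six muscle comparisons at a literal 1% carry about 4.8%.
- A reader might infer that no family of contrasts is named. Section 10.0 does name one, every pair, and corrects it in the same sentence. What remains is the tension with the spironolactone label in section 2.0.
- A reader might infer that skin and muscle are settled as two separate primary endpoints, so that twelve tests must be corrected and the trial is underpowered. That is one reading. The sizing suggests muscle alone, and the wording in section 2.0 also allows a requirement that both tissues fall. Neither of these needs alpha divided between tissues.

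The objection does not remove the two wrong printed figures or the absence of any statement on how skin enters the correction.

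**Conclusion.** The point holds in a limited form. Given a 5% family-wise level, six pairwise tests require 0.83%, and 41 per group requires 164 in total. Both printed figures should be corrected, although for muscle alone neither changes the error rate or power in a way that matters.

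The status of skin is the more consequential gap. If all six pairs are confirmatory in each tissue, family-wise error is about 7–8% at 0.83% and 8.5–9.5% at 1%. Correcting all twelve tests lowers power at 41 per arm from 85.4% to 79.1%. These figures rest on an assumed tissue correlation of 0.7 to 0 and on skin having the same standardised effect as muscle; the documents give no effect or SD for skin. Power would be 88.8% at 50 per arm, but that needs all 200 to be randomised equally. Section 5.0 also enrols subjects only through Week 0 and does not say whether they count in the 200.

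**What to change.** 1. For the six-pair muscle analysis that section 10.0 sizes, state the 5% family-wise level, test each pair at 0.05/6 = 0.83%, and print 164.
2. State whether skin Na+ is a separate primary endpoint, a co-primary that must succeed together with muscle, or secondary. Do this before any Na+ result is viewed by arm. The timing matters because the diet arm is open: "The design is a randomized, double-blind (except for those in the diet group), placebo-controlled study".
3. Reconcile the every-pair family in section 10.0 with the spironolactone label in section 2.0, and name the comparator. Section 2.0 names hydrochlorothiazide and sections 5.0 and 6.0 name chlorthalidone; these passages must also be reconciled so that the contrasts refer to the arms actually randomised.
4. Let the divisor follow from those choices:
   - All six pairs, each confirmatory in each tissue: use 0.05/12 and restate power as 79% at 41 per arm. At 46 per arm (184 in total) it returns to 85%, if skin has the same standardised effect.
   - A smaller family: divide by its own number of tests. Three active arms against placebo in both tissues is again six tests, so 0.83%, 41 and 164 stay as they are.

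The cost is text edits. The downside is that contrasts or tissues left outside the family become secondary and cannot carry a confirmatory claim, or that the stated power drops somewhat if everything is kept.

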- Specific Aim 4:** To test the hypothesis that the accumulation of salt in skin and muscle is associated with decreased insulin sensitivity and propensity to diabetes mellitus (Secondary Outcome)

[figure not shown]

Fig. 2. Proposed cohort for the study of the relationship between tissue Na+ storage and cardiovascular disease. Cross-sectional analysis will primarily address the effect of race on tissue Na+ content. We hypothesize that African Americans have increased skin Na+ storage, which is associated with increased arterial stiffness and higher blood pressure (Aim 1). In a proof-of-concept approach, we then will prospectively test the hypothesis that diet or drug intervention for 8 weeks can lower tissue Na+ content (Aim 2). Finally, we will test the hypothesis that subjects with increased tissue Na+ content show pro-inflammatory immune-cell polarization (cooperation with basic science project), and reduced insulin sensitivity (Aim 3).

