*Preliminary data from Na MRI pilot studies.* In European Caucasians, we have shown earlier that tissue Na+ content increases with age. Controlled for age, tissue Na+ is further elevated in patients with refractory hypertension. We now have prospectively screened skin Na+, muscle Na+, and systolic blood pressure in 34 men (age: 55.8±16.2 years) and in 24 women (age: 44.8±14.1 years) to investigate the effect of age and gender on tissue Na+ content and blood pressure in humans. We have confirmed that blood pressure continuously increases with age, albeit at lower levels in women (Fig. 10A). Interestingly, we found a very similar increase in skin Na+ content with age, which again was more pronounced in men than in women (Fig. 10B), while increases in skin Na+ content were associated with parallel, as if dose-dependent, increases in blood pressure in both sexes (Fig. 10C). Skin Na+ content explained more of the variability in blood pressure than age, especially in men. Based on these preliminary data, we hypothesize that tissue Na+ accumulation may be a relevant and potentially reversible pathophysiological component for the development of hypertension in the aging population. This hypothesis leads to 3 subsequent questions. *First*, are populations with a higher incidence of hypertension (African Americans) characterized by higher tissue Na+ content? *Second*, could tissue Na+ content be therapeutically modified to attenuate the age-dependent increase in tissue Na+ content? *Third*, will successful reduction of tissue Na+ content lower blood

pressure and reduce pulse wave velocity (PWV)? We will address these questions in a prospective, double-blinded, randomized controlled trial on the efficacy of diet and different drugs to lower tissue Na+ content (Aim 2).

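### Aim 1's primary endpoint, tissue Na+ by race, has no planned test: Section 10.0 powers and tests only the secondary variables, without age adjustment

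*Combined protocol and SAP*

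**What the plan says.** Section 2.0 sets the endpoint hierarchy. Tissue Na+ "content will be our primary endpoint in Aims 1 and 2. As secondary endpoints, we will read out differences in blood pressure", and that list of secondary endpoints goes on to forearm blood flow and PWV. Specific Aim 1 opens "To test the hypothesis that African Americans are characterized by increased tissue" Na+ storage, and then adds the blood pressure, blood flow and PWV differences as features expected to run in parallel. The legend to Fig. 2 in the same section says "Cross-sectional analysis will primarily address the effect of race on tissue" Na+ content, and continues "We hypothesize that African Americans have increased skin" Na+ storage. Section 3.0 puts the same comparison first among its three questions: "are populations with a higher incidence of hypertension (African Americans) characterized by higher tissue" Na+ content?

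The Aim 1 text of Section 10.0 has three elements:

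- **Power:** 100 per race group "provides 85% power to detect an effect size of 0.42 in blood pressure, forearm blood flow or PWV" at two-sided 5%.
- **Summaries:** the same three variables at Week 0, by race.
- **Test:** "We will test the difference of these variables among two race group using two sample t-test".

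On age, Section 2.0 says that the cohort will be controlled for gender, race and age. The readable text of Section 5.0 balances enrolment on race and gender only, and stratifies the randomisation on those two factors.

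**The concern.** In the test sentence, the variables referred to are the three just summarised. Tissue Na+ is not among them, so a statistician who follows Section 10.0 to the letter would finish Aim 1 without comparing its primary endpoint between the race groups. If the comparison is added later, the tissue (skin or muscle), the covariates and the significance level would be chosen with the data in hand.

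The lesser concern is age. Race is not assigned by randomisation, so randomising treatment does nothing to balance age between the race groups. Eligible ages run from 30 to 80 years (Section 4.0). Section 1.0 says that tissue Na+, blood pressure and PWV all rise with age. An unadjusted race difference in any of them could partly be an age difference.

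**Working it through.** **1. Where tissue Na+ is analysed in Section 10.0**

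| Aim | Analysis | Race comparison of tissue Na+? |
|---|---|---|
| 1 | Two-sample t-tests of blood pressure, forearm blood flow, PWV | No; tissue Na+ not listed |
| 2 | Pairwise t-tests of tissue Na+ between treatment groups; partial linear model for the treatment effect | No; comparison is by treatment |
| 3 | Correlation of change in Na+ with change in immune activity; regression with covariates | No; about changes |
| 4 | As Aim 3, with change in insulin sensitivity | No; about changes |

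Planned race tests of tissue Na+: 0. Planned race tests of variables listed as secondary: 3.

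**2. Where age adjustment appears**

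The Aim 2 model adjusts for age and gender. The Aim 3 regression, reused for Aim 4, adjusts for age, sex and body weight. The Aim 1 t-tests adjust for nothing.

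**3. Reproducing the stated power**

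Inputs from Section 10.0: n = 100 per group, standardised difference d = 0.42, two-sided alpha 0.05.

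- Noncentrality: d × √(n/2) = 0.42 × √50 = 2.970.
- Normal approximation: Φ(2.970 − 1.960) = Φ(1.010) = 84.4%.
- Noncentral t: 84.0%.
- n per group for 85% power: 2 × (1.960 + 1.036)² / 0.42² = 101.8, so 102 (103 by the t-test).

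The stated 85% with 100 per group agrees to within rounding.

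**4. Carrying the figure over to tissue Na+**

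The effect size is in SD units, so the calculation is the same for one tissue Na+ endpoint:

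- Power at 0.42 SD: 84.0%.
- Difference detectable with 85% power: (1.960 + 1.036) × √(2/100) = 0.424 SD (normal), 0.426 SD (t-test).
- Skin and muscle co-primary at 2.5% each: power at 0.42 SD is 76.1% per tissue (t-test).

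**5. Effect of age adjustment on power**

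If age is balanced between the race groups and correlates r with the outcome, adjustment shrinks the residual SD by √(1 − r²), so the effective difference becomes 0.42/√(1 − r²). The documents give no r. For assumed values:

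| r (assumed) | Power at 0.42 SD | Detectable difference at 85% power |
|---|---|---|
| 0.3 | 87.2% | 0.41 SD |
| 0.5 | 92.7% | 0.37 SD |
| 0.7 | 98.5% | 0.30 SD |

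The unadjusted 84% is therefore a conservative figure for an age-adjusted analysis when age is balanced. An age gap between the groups would give back some of the gain.

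**The case against.** The three tested variables are not foreign to Aim 1: its hypothesis names them. A reader might infer that Aim 1 is not tested at all, and that would go too far. The parallel features are tested; the lead clause on Na+ storage is not. The objection narrows the point but does not remove it, because Section 2.0 ranks these variables below tissue Na+.

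The age point is weaker. Section 2.0 promises age control, and the cohort figure in Section 2.0 and the figure in Section 5.0 are not shown in the text available, so either may say how it is done. The authors also plainly considered age under Aims 2 and 3. A reader might still infer that the unadjusted t-tests will have an inflated false-positive rate. The documents do not support that. The spurious difference would be about r × (age gap)/(age SD), and neither the correlation nor a race gap in age is given. The pilot in Section 3.0 reports age SDs of 16.2 years in men and 14.1 in women, but all its subjects were Caucasian and it says nothing about age by race. If age is controlled as promised, there is no systematic gap.

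Two further inferences also fail. The trial is not too small for the missing test, as the power check shows. Nor is the randomised comparison undermined: the aims list attaches the primary-outcome label to Aim 2, and tissue Na+ is tested there.

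**Conclusion.** The point stands and should be fixed. Section 10.0 omits the race comparison of tissue Na+ that Sections 2.0 and 3.0 make the main question of Aim 1: no planned tests of the primary endpoint, against three of variables listed as secondary. This rests on the text alone and needs no numerical assumption.

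The lack of age adjustment is a subordinate weakness of a non-randomised comparison. Its effect depends on an age gap that the documents do not give, so no error rate is attached to it.

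The power figures assume 100 analysed subjects per race group. That number is not fully settled, because Section 5.0 also enrols subjects who attend only through Week 0, for Aims 1, 3 and 4, and does not say whether they count towards the 100.

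**What to change.** In Section 10.0:

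- Make the Aim 1 primary analysis the race difference in Week 0 tissue Na+, by linear regression on race adjusted for age and sex, with a 95% confidence interval and a two-sided 5% test.
- Have the sponsor name one primary tissue in advance and make the other secondary. Skin would match the Fig. 2 legend; muscle would match the Aim 2 power statement. The documents do not settle the choice.
- Label blood pressure, forearm blood flow and PWV as secondary for Aim 1, with the same adjustment.
- Attach the power statement to tissue Na+: with 100 per group, about 84% at 0.42 SD, or 85% at about 0.43 SD, by unadjusted t-test. Describe it as conservative for the adjusted analysis if age is balanced between the race groups. If both tissues are to be co-primary at 2.5% each, state about 76% instead.
- Say whether Week-0-only subjects count towards the 100 per group.

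A sentence in Section 5.0 should reconcile its recruitment controls with the age control promised in Section 2.0.

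The cost is text in two sections and one sponsor decision. Week 0 <sup>23</sup>NaMRI and demographics are already collected (Section 6.0), so no new data, visits or subjects are needed.
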